5.6 Discussion and Justification of Study Design

5.6.1 Discussion of Study Design and Choice of Control Groups

This study includes two periods.

Period 1 is a 12-week, randomized, double-blind, placebo-controlled period to compare safety and efficacy of upadacitinib versus placebo in subjects with moderately to severely active RA who are on a stable dose of csDMARDs and have an inadequate response to csDMARDs. Period 1 is designed to test superiority of upadacitinib versus placebo for achieving the primary endpoint (ACR20 for US/FDA regulatory purposes or LDA for EU/EMA regulatory purposes) at Week 12, and other secondary efficacy parameters, all on a stable background csDMARD therapy.

The purpose of Period 2 is to evaluate the long-term safety, tolerability, and efficacy of upadacitinib 30 mg QD and 15 mg QD in a blinded fashion in subjects with RA who have completed Period 1. Subjects who are assigned to upadacitinib treatment groups in Period 1 will continue to receive upadacitinib 15 mg QD or 30 mg QD per original randomization assignment in a blinded manner. Subjects who are assigned to placebo in Period 1 will be switched to receive upadacitinib 15 mg or 30 mg QD in a blinded fashion per pre-specified randomization assignments. Preventing dose reduction or escalation of upadacitinib during Period 2 will allow better assessments of long-term safety and efficacy of upadacitinib 15 mg QD versus 30 mg QD.

Starting with Amendment 6, all subjects will receive open-label upadacitinib 15 mg QD, including those currently on upadacitinib 30 mg QD.

5.6.2 Appropriateness of Measurements

Standard statistical, clinical, and laboratory procedures will be utilized in this study. All efficacy measurements in this study are standard for assessing disease activity in subjects with RA. All clinical and laboratory procedures in this study are standard and generally accepted.

5.6.3 Suitability of Subject Population

The intended study population is moderately to severely active RA patients who have had an inadequate response to prior csDMARD treatment. Key entry criteria are to enroll adult female and male subjects who are at least 18 years of age with a diagnosis of RA for ≥ 3 months who also fulfill the 2010 ACR/EULAR classification criteria for RA. Eligible study subjects must have ≥ 6 swollen joints (based on 66 joint counts) and ≥ 6 tender joints (based on 68 joint counts) at Screening and Baseline Visits, and hsCRP ≥ 3 mg/L (central lab) at Screening. Subjects must have been on a stable dose of csDMARD therapy (restricted to MTX, chloroquine, hydroxychloroquine, sulfasalazine, or leflunomide) for ≥ 4 weeks prior to the first dose of study drug. Subjects with inadequate response to hydroxychloroquine and/or chloroquine can only be included if they also failed MTX, sulfasalazine, or leflunomide.

5.6.4 Selection of Doses in the Study

Two doses of the once-daily formulation of upadacitinib will be evaluated: upadacitinib 15 mg QD and 30 mg QD. The dose selection in this study is based on extrapolation of pre-clinical efficacy models and analyses of PK, pharmacodynamic, safety, and efficacy data from the Phase 1 studies in healthy volunteers (single and multiple ascending dose Studies M13-401 and M13-845, respectively) and Phase 2 studies in RA subjects (Studies M13-537 and M13-550). The doses selected for Study M13-549, upadacitinib 15 mg QD and 30 mg QD, dosed for up to 260 weeks, are expected to be efficacious with an acceptable safety profile.

Doses of 15 mg QD and 30 mg QD using the once-daily formulation provide equivalent daily AUC and comparable C_{max} and C_{min} to 6 mg BID and 12 mg BID, respectively, of the immediate-release formulation tested in Phase 2 studies in subjects with RA. In Phase 2 studies, the 6 mg BID dose was shown to achieve the near maximum efficacy and the 12 mg BID dose was clearly shown to achieve the plateau of efficacy.

6.0 Complaints

A Complaint is any written, electronic, or oral communication that alleges deficiencies related to the physical characteristics, identity, quality, purity, potency, durability, reliability, safety, effectiveness, or performance of a product/device after it is released for distribution.

Complaints associated with any component of this investigational product must be reported to the Sponsor (Section 6.2.2). For AEs, please refer to Section 6.1. For product complaints, please refer to Section 6.2.

6.1 Medical Complaints

The Investigator will monitor each subject for clinical and laboratory evidence of AEs on a routine basis throughout the study. The Investigator will assess and record any AE in detail including the date of onset, event diagnosis (if known) or sign/symptom, severity, time course (end date, ongoing, intermittent), relationship of the AE to study drug, and any action(s) taken. For SAEs considered as having "no reasonable possibility" of being associated with study drug, the Investigator will provide other cause(s) of the event. For AEs to be considered intermittent, the events must be of similar nature and severity. AEs, whether in response to a query, observed by site personnel, or reported spontaneously by the subject will be recorded.

All AEs will be followed to a satisfactory conclusion.

6.1.1 Definitions

6.1.1.1 Adverse Event

An AE is defined as any untoward medical occurrence in a patient or clinical investigation subject administered a pharmaceutical product and which does not necessarily have a causal relationship with this treatment. An AE can therefore be any unfavorable and unintended sign (including an abnormal laboratory finding), symptom, or disease

temporally associated with the use of a medicinal (investigational) product, whether or not the event is considered causally related to the use of the product.

Such an event can result from use of the drug as stipulated in the protocol or labeling, as well as from accidental or intentional overdose, drug abuse, or drug withdrawal. Any worsening of a pre-existing condition or illness is considered an AE. Worsening in severity of a reported AE should be reported as a new AE. Laboratory abnormalities and changes in vital signs are considered to be AEs only if they result in discontinuation from the study, necessitate therapeutic medical intervention, and/or if the investigator considers them to be AEs.

An elective surgery/procedure scheduled to occur during the study will not be considered an AE if the surgery/procedure is being performed for a pre-existing condition and the surgery/procedure has been pre-planned prior to study entry. However, if the pre-existing condition deteriorates unexpectedly during the study (e.g., surgery performed earlier than planned), then the deterioration of the condition for which the elective surgery/procedure is being done will be considered an AE.

6.1.1.2 Serious Adverse Events

If an AE meets any of the following criteria, it is to be reported to AbbVie as an SAE within 24 hours of the site being made aware of the SAE.

Death of Subject	An event that results in the death of a subject.
Life-Threatening	An event that, in the opinion of the investigator, would have resulted in immediate fatality if medical intervention had not been taken. This does not include an event that would have been fatal if it had occurred in a more severe form.
Hospitalization or Prolongation of Hospitalization	An event that results in an admission to the hospital for any length of time or prolongs the subject's hospital stay. This does not include an emergency room visit or admission to an outpatient facility.
Congenital Anomaly	An anomaly detected at or after birth, or any anomaly that results in fetal loss.

Persistent or Significant Disability/Incapacity	An event that results in a condition that substantially interferes with the activities of daily living of a study subject. Disability is not intended to include experiences of relatively minor medical significance such as headache, nausea, vomiting, diarrhea, influenza, and accidental trauma (e.g., sprained ankle).
Important Medical Event Requiring Medical or Surgical Intervention to Prevent Serious Outcome	An important medical event that may not be immediately life-threatening or result in death or hospitalization, but based on medical judgment may jeopardize the subject and may require medical or surgical intervention to prevent any of the outcomes listed above (i.e., death of subject, life-threatening, hospitalization, prolongation of hospitalization, congenital anomaly, or persistent or significant disability/incapacity). Additionally, any elective or spontaneous abortion or stillbirth is considered an important medical event. Examples of such events include allergic bronchospasm requiring intensive treatment in an emergency room or at home, blood dyscrasias or convulsions that do not result in inpatient hospitalization, or the development of drug dependency or drug abuse.

For SAEs with the outcome of death, the date and cause of death will be recorded on the appropriate case report form.

6.1.1.3 Adverse Events of Special Interest

The following AEs of special interest will be monitored during the study (see detailed toxicity management in Section [6.1.7](#)):

- Serious infections;
- Opportunistic infections;
- Herpes zoster;
- Active tuberculosis;
- Malignancy (all types);
- Adjudicated Gastrointestinal perforations;

- Adjudicated cardiovascular events (e.g., major adverse cardiovascular event [MACE]);
- Anemia;
- Neutropenia;
- Lymphopenia;
- Increased serum creatinine and renal dysfunction;
- Hepatic events and increased hepatic transaminases;
- Increased creatine phosphokinase (CPK);
- Adjudicated embolic and thrombotic events (non-cardiac, non-CNS).

6.1.2 Adverse Event Severity

The investigator will classify AEs according to the Rheumatology Common Toxicity Criteria v.2.0 ([Appendix N](#)).²²

6.1.3 Relationship to Study Drug

The Investigator will use the following definitions to assess the relationship of the AE to the use of study drug:

Reasonable Possibility	After consideration of factors including timing of the event, biologic plausibility, clinical judgment, and potential alternative causes, there is sufficient evidence (information) to suggest a causal relationship.
No Reasonable Possibility	After consideration of factors including timing of the event, biologic plausibility, clinical judgment, and potential alternative causes, there is insufficient evidence (information) to suggest a causal relationship.

For causality assessments, events assessed as having a reasonable possibility of being related to the study drug will be considered "associated." Events assessed as having no reasonable possibility of being related to study drug will be considered "not associated."

In addition, when the investigator has not reported a relationship or deemed it not assessable, AbbVie will consider the event associated.

[figure not shown]
If an Investigator's opinion of no reasonable possibility of being related to study drug is given, an Other cause of event must be provided by the investigator for the serious adverse event.

6.1.4 Adverse Event Collection Period

All AEs reported from the time of study drug administration until 30 days following discontinuation of study drug administration have elapsed will be collected, whether solicited or spontaneously reported by the subject. Subjects who discontinue study drug treatment but continue to participate in the study will have SAEs and non-serious AEs collected for the remainder of study participation. In addition, SAEs and protocol-related nonserious AEs will be collected from the time the subject signed the study-specific informed consent.

Adverse event information will be collected as shown in [Figure 4](#).

Figure 4. Adverse Event Collection

* Subjects who discontinue study drug but continue to participate in the study will have SAEs and Non serious AEs collected for the remainder of study participation.

Additionally, in order to assist the adjudication process, additional information on any potential cardiovascular events including thromboembolic events will be collected, if applicable.

In the case of any of the following reported events, an appropriate supplemental eCRF should be completed:

- Cardiac events;
- Myocardial infarction or unstable angina;
- Heart failure;
- Cerebral vascular accident and transient ischemic attack;
- Cardiovascular procedures (SAE Supplemental Procedure eCRF)
- Embolic and thrombotic events (non-cardiac, non-CNS).
- Hepatic;
- Renal;
- Herpes Zoster Infection;
- CPK increases considered by the investigator to be an AE;
- COVID-19

Supplemental study case report forms should be completed in the event of COVID-19 related missed/virtual visits, study drug interruptions or discontinuations, or adverse events (including documentation of specific signs/symptoms of infection and testing results).

COVID-19 infections should be captured as adverse events. If the event meets the criteria for a serious adverse event (SAE), then follow the SAE reporting directions per the protocol and above.

The following COVID-19 related supplemental eCRFs should be completed (for both serious and non-serious events):

- COVID-19 Supplemental Signs/ Symptoms

- COVID-19 Status Form

6.1.6 Pregnancy

Pregnancy in a study subject must be reported to AbbVie within 24 hours after the site becomes aware of the pregnancy. Subjects who become pregnant during the study must be discontinued from study drug (Section 5.4.1).

Information regarding a pregnancy occurrence in a study subject and the outcome of the pregnancy will be collected.

Pregnancy in a study subject is not considered an AE. However, the medical outcome of an elective or spontaneous abortion, stillbirth, or congenital anomaly is considered an SAE and must be reported to AbbVie within 24 hours of the site becoming aware of the event.

Subjects should avoid pregnancy throughout the course of the study, starting with the Screening Visit through 30 days after the last study drug administration. Refer to [Appendix O](#) for local requirements for Canada. Results of a positive pregnancy test or confirmation of a pregnancy will be assessed starting with the Screening Visit through the final study visit.

6.1.7 Toxicity Management

The toxicity management of the AEs including AEs of special interest consists of safety monitoring (review of AEs on an ongoing basis, and periodical/ad hoc review of safety issues by a safety data monitoring committee), interruption of study drug dosing with appropriate clinical management if applicable, and discontinuation of the subjects from study drug. The management of specific AEs and laboratory parameters is described below.

For subjects who discontinued study drug but continued study participation and are on standard of care therapies, these toxicity management requirements do not apply (including alerts from the central lab) and any intolerability to standard of care therapies should be managed by the prescribing physician.

Serious Infections: Subjects should be closely monitored for the development of signs and symptoms of infection during and after treatment with study drug. Study drug should be interrupted if a subject develops a serious infection or an opportunistic infection. A subject who develops a new infection during treatment with study drug should undergo prompt diagnostic testing appropriate for an immunocompromised subject. As

appropriate, antimicrobial therapy should be initiated, and the subject should be closely monitored. Re-challenge with study drug may occur once the infection has been successfully treated. If study drug has been interrupted for a serious infection for more than 7 consecutive days during the first 24 weeks of the study or 30 consecutive days thereafter, the subject must be discontinued from study drug. Subjects who develop active TB must be discontinued from study drug.

COVID-19: Interrupt study drug in subjects with a confirmed diagnosis of COVID-19. Consider interrupting study drug in subjects with signs and/or symptoms and suspicion of COVID-19. The COVID-19 eCRF must be completed.

Herpes zoster: If a subject develops herpes zoster, consider temporarily interrupting study drug until the episode resolves.

Gastrointestinal Perforation: If a diagnosis of gastrointestinal perforation is confirmed (other than appendicitis or penetrating injury), the subject must be permanently discontinued from study drug.

Cardiovascular Events (MACE): Subjects presenting with potential cardiovascular events should be carefully monitored. These events will be reviewed and adjudicated by an independent Cardiovascular Adjudication Committee in a blinded manner.

Thrombosis Events: Subjects who develop symptoms of thrombosis should be promptly evaluated and treated appropriately. If the diagnosis of deep vein thrombosis, pulmonary embolus or non-cardiac, non-neurologic arterial thrombosis is confirmed, the subject must be discontinued from study drug.

Malignancy: Subjects who develop malignancy other than NMSC or carcinoma in-situ of the cervix must be discontinued from study drug. Information including histopathological results should be queried for the confirmation of the diagnosis. Periodic skin examination is recommended for subjects who are at increased risk for skin cancer.

ECG Abnormality: Subjects must be discontinued from study drug for an ECG change considered clinically significant and with reasonable possibility of relationship to study drug OR a confirmed absolute QTcF value > 500 msec.

Management of Select Laboratory Abnormalities: For any given laboratory abnormality, the Investigator should assess the subject, apply the standard of care for medical evaluation and treatment following any local guidelines. Specific toxicity management guidelines for abnormal laboratory values are described in [Table 7](#) and may require an appropriate supplemental eCRF to be completed. All abnormal laboratory tests that are considered clinically significant by the Investigator will be followed to a satisfactory resolution. If a repeat test is required per [Table 7](#), the repeat testing must occur as soon as possible.

Table 7. Specific Toxicity Management Guidelines for Abnormal Laboratory Values

Laboratory Parameter	Toxicity Management Guideline
Hemoglobin	
 • If hemoglobin < 8 g/dL, interrupt study drug dosing and confirm by repeat testing with new sample. • If hemoglobin decreases \geq 3.0 g/dL from baseline without an alternative etiology, interrupt study drug dosing and confirm by repeat testing with new sample. • If hemoglobin decreases \geq 3.0 g/dL from baseline and an alternative etiology is known, the subject may remain on study drug at the investigator's discretion. • If confirmed, continue to withhold study drug until hemoglobin value returns to normal reference range or its baseline value.
Absolute neutrophil count (ANC)	
 • If confirmed < 1000 cells/μL by repeat testing with new sample, interrupt study drug dosing until ANC value returns to normal reference range or its baseline value. • Discontinue study drug if confirmed < 500 cells/μL by repeat testing with new sample.
Absolute lymphocyte counts (ALC)	
 • If confirmed < 500 cells/μL by repeat testing with new sample, interrupt study drug dosing until ALC returns to normal reference range or its baseline value.
Total white blood cell count	
 • If confirmed < 2000 cells/μL by repeat testing with new sample, interrupt study drug dosing until white blood cell count returns to normal reference range or its baseline value.
Platelet count	
 • If confirmed < 50,000 cells/μL by repeat testing with new sample, interrupt study drug dosing until platelet count returns to normal reference range or its baseline value.

Table 7. Specific Toxicity Management Guidelines for Abnormal Laboratory Values (Continued)

Laboratory Parameter	Toxicity Management Guideline
AST or ALT	
 • Interrupt study drug immediately if confirmed ALT or AST > 3 × ULN by repeat testing with new sample and either a total bilirubin > 2 × ULN or an international normalized ratio (INR) > 1.5. 
 ○ A separate blood sample for INR testing will be needed to measure INR at the time of repeat testing for ALT or AST. A repeat test of INR is not needed for determination if above toxicity management criteria are met. • Interrupt study drug immediately if confirmed ALT or AST > 3 × ULN by repeat testing with new sample along with appearance of fatigue, nausea, vomiting, right upper quadrant pain or tenderness, fever, rash, and/or eosinophilia (> 5%). • Interrupt study drug immediately if confirmed ALT or AST > 5 × ULN by repeat testing with new sample for more than 2 weeks. • If ALT or AST > 8 × ULN, interrupt study drug immediately, confirm by repeat testing with a new sample, and contact the TA MD. 
Subjects who meet any of the above criteria should be evaluated for an alternative etiology of the ALT or AST elevation and managed as medically appropriate. If applicable, the alternative etiology should be documented in the eCRF. If ALT or AST values return to the normal reference range or its Baseline value, study drug may be restarted. If restarting study drug, documentation should include reason that rechallenge is expected to be safe. If after clinically appropriate evaluation, no alternative etiology for ALT or AST elevation is found or the ALT or AST elevation has not resolved or is not trending down toward normal, the subject should be discontinued from study drug.
 
 • For subjects with HBc Ab+ (irrespective of HBs Ab status) and negative HBV DNA at screening who develop the following should have HBV DNA by PCR testing performed within one week: 
 ○ ALT > 5 × ULN OR ○ ALT or AST > 3 × ULN if an alternative cause is not readily identified. ○ A positive result for HBV DNA PCR testing in these subjects will require immediate interruption of study drug and a hepatologist consultation should occur within one week for recommendation regarding subsequent treatment. 
For any confirmed ALT or AST elevations > 3 ULN, complete supplemental hepatic eCRF.

Serum Creatinine	
 • If serum creatinine is > 1.5 × the baseline value and > ULN, repeat the test for serum creatinine (with subject in an euvoletic state) to confirm the results. If the results of the repeat testing still meet this criterion, then interrupt study drug and re-start study drug once serum creatinine returns to ≤ 1.5 × baseline value and ≤ ULN. • If confirmed serum creatinine ≥ 2 mg/dL, interrupt study drug and re-start study drug once serum creatinine returns to normal reference range or its baseline value. 
For the above serum creatinine elevation scenarios, complete supplemental renal eCRF.

Table 7. Specific Toxicity Management Guidelines for Abnormal Laboratory Values (Continued)

Laboratory Parameter	Toxicity Management Guideline
Creatine Phosphokinase	
 • If confirmed CPK value $\geq 4 \times$ ULN and there are no symptoms suggestive of myositis or rhabdomyolysis, the subjects may continue study drug at the investigator's discretion. • If CPK $\geq 4 \times$ ULN accompanied by symptoms suggestive of myositis or rhabdomyolysis, interrupt study drug and contact AbbVie TA MD. 
For the above CPK elevation scenarios, complete supplemental CPK eCRF.

For allowed study drug interruption, the following rules apply:

Period 1

- Allow study drug interruption up to 7 consecutive days for AEs and emergency surgery. Elective surgery will not be allowed during this 12 week-period.
- If the subject must undergo emergency surgery, the study drug should be interrupted at the time of the surgery. After emergency surgery, allow reintroduction of study drug once the physician has examined the surgical site and determined that it has healed and there is no sign of infection.

Period 2

- Allow study drug interruption up to 7 consecutive days for AEs and emergency surgery up until the Week 24 visit in Period 2, and after Week 24 and thereafter, up to 30 consecutive days of study drug interruption is allowed. The Investigator will make determination if study drug should be restarted for interruptions > 30 days.
- Elective surgery is allowed starting at Week 24 in Period 2. If the subject undergoes elective surgery, the study drug should be interrupted 1 week prior to the planned surgery. Allow reintroduction of study drug once the physician has examined the surgical site and determined that it has healed and there is no sign of infection.
- If the subject must undergo emergency surgery, the study drug should be interrupted at the time of surgery. Allow reintroduction of study drug once the

physician has examined the surgical site and determined that it has healed and there is no sign of infection.

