Safety data from these two studies (N = 575) showed that the types and frequencies of AEs during upadacitinib treatment were consistent with subjects with moderately to severely active RA receiving immunomodulatory therapy. The incidences of AEs were numerically higher in the upadacitinib dose groups, with a trend toward higher rates with higher doses of upadacitinib. The most frequently reported AEs ($\geq 5\%$) in the upadacitinib treated subjects were urinary tract infection, headache, upper respiratory tract infection, and nausea. There were 6 subjects (1.3% of total combined populations) with herpes zoster reactivation distributed across the upadacitinib dose groups, and 2 subjects (1.9%) in the placebo groups. In these two 12 week studies, a total of 2 subjects in the upadacitinib treatment groups reported malignancies. One subject reported non-melanoma skin cancers (NMSC) (basal cell and squamous cell carcinoma) and 1 subject was diagnosed with lung cancer after the final scheduled visit, and subsequently died 14 weeks after study completion. These events were reported by the Investigators as not possibly related to study drug. Elevations of liver function tests were sporadic with no clear dose-response relationship observed. As observed with other JAK inhibitors, treatment with upadacitinib resulted in an increase in lipids (low-density lipoprotein cholesterol [LDL-C] and high-density lipoprotein cholesterol [HDL-C]). Among subjects with laboratory evidence of systemic inflammation (as evidenced by high-sensitivity C-reactive protein [hsCRP] > upper limit of normal [ULN]), treatment with lower doses of upadacitinib (3 mg BID and 6 mg BID) was associated with improvements in mean hemoglobin relative to placebo. At higher doses, there was a reduction in mean hemoglobin; however, the mean hemoglobin levels remained within normal range throughout the treatment period.

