 10. Systemic use of known strong cytochrome P450 (CYP) 3A inhibitors or strong CYP3A inducers from Screening through the end of the study (refer to Table 1 for examples of commonly used strong CYP3A inhibitors and inducers).
 11. Receipt of any live vaccine within 4 weeks prior to the first dose of study drug, or expected need of live vaccination during study participation including at least 4 weeks after the last dose of study drug.
 12. History of any malignancy except for successfully treated NMSC or localized carcinoma in situ of the cervix.
 13. History of clinically significant (per Investigator's judgment) drug or alcohol abuse within the last 6 months.
 14. History of gastrointestinal perforation or a history of associated gastrointestinal diseases including but not limited to diverticulitis and gastroduodenal ulcers.
 15. Conditions that could interfere with drug absorption including but not limited to short bowel syndrome.
 16. Subject has been a previous recipient of an organ transplant.
 17. History of clinically significant medical conditions or any other reason that in the opinion of the Investigator would interfere with the subject's participation in this study or would make the subject an unsuitable candidate to receive study drug.
 18. Infection(s) requiring treatment with parenteral anti-infectives within 30 days, or oral anti-infectives within 14 days prior to the first dose of study drug.
 19. History of an allergic reaction or significant sensitivity to constituents of the study drug (and its excipients) and/or other products in the same class.

20. Laboratory values meeting the following criteria within the Screening period prior to the first dose of study drug:
- Serum aspartate transaminase (AST) $> 2 \times$ ULN;
 - Serum alanine transaminase (ALT) $> 2 \times$ ULN;
 - Estimated glomerular filtration rate (GFR) by simplified 4-variable Modification of Diet in Renal Disease (MDRD) formula < 40 mL/min/1.73 m²;
 - Total white blood cell (WBC) count $< 2,500/\mu\text{L}$;
 - Absolute neutrophil count (ANC) $< 1,500/\mu\text{L}$;
 - Platelet count $< 100,000/\mu\text{L}$;
 - Absolute lymphocyte count $< 850/\mu\text{L}$;
 - Hemoglobin < 10 g/dL.

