J2. Cough	Transient, intermittent, occasional OTC meds relieve	Persistent, requires narcotic or other prescription meds for relief	Recurrent, persistent coughing spasms without consistent relief by meds, interferes with function	Interferes with oxygenation; debilitating
J3. Dyspnea	Subjective, transient, no interference with function	Symptomatic, intermittent or recurring, interferes with exertional activities	Symptomatic during daily routine activities, interferes with function, treatment with intermittent nasal O ₂ relieves	Symptomatic at rest, debilitating, requires constant nasal O ₂
J4. Pleuritic pain (pleurisy)	Transient, intermittent symptoms, no treatment or OTC meds relieve	Persistent symptoms, requires prescription meds for relief	Prolonged symptoms, interferes with function, requires frequent narcotic pain relief	Debilitation, requiring hospitalisation
J5. Pneumonitis (pulmonary infiltrates)	Asymptomatic radiographic changes, transient, no treatment required	Symptomatic, persistent, requiring corticosteroids	Symptomatic, requiring treatment including O ₂	Debilitating, not reversible; or requiring assisted ventilation
J6. Pulmonary function decreased (FVC or carbon monoxide diffusion capacity – DLCO)	76% – 90% of pre-treatment value	51% – 75% of pre-treatment value	26% – 50% of pre-treatment value	≤ 25% of pre-treatment value

Laboratory Data				
K. Haematology				
K1. Hgb (g/dl) decrease from pre-treatment	1.0 – 1.4	1.5 – 2.0	2.1 – 2.9, or Hgb < 8.0, > 7.0	≥ 3.0; or Hgb < 7.0
K2. Leukopenia (total WBC) × 1000	3.0 – 3.9	2.0 – 2.9	1.0 – 1.9	< 1.0
K3. Neutropenia (× 1000)	1.5 – 1.9	1.0 – 1.4	0.5 – 0.9	< 0.5
K4. Lymphopenia (× 1000)	1.5 – 1.9	1.0 – 1.4	0.5 – 0.9	< 0.5
K5. Platelets (× 1000)	75 – LLN	50 – 74.9	20 – 49.9; platelet transfusion required	< 20; recurrent platelet transfusions required
L. Chemistry				
L1. Hypercalcaemia (mg/dl)	1.1 × ULN – 11.5	11.6 – 12.5	12.6 – 13.5; or symptoms present	> 13.5; or associated coma
L2. Hyperglycemia (mg/dl) Fasting	140 – 160	161 – 250	251 – 500	> 500, or associated with ketoacidosis
L3. Hyperkalaemia (mg/dl)	5.5 – 5.9	6.0 – 6.4	6.5 – 7.0 or any ECG change	> 7.0 or any arrhythmia
L5. Hypocalcaemia (mg/dl)	0.9 × LLN – 7.8	7.7 – 7.0	6.9 – 6.5; or associated with symptoms	< 6.5 or occurrence of tetany
L6. Hypoglycemia (mg/dl)	55 – 64 (no symptoms)	40 – 54 (or symptoms present)	30 – 39 (symptoms impair function)	< 30 or coma
L7. Hyponatraemia (mg/dl)	--	125 – 129	120 – 124	< 120

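### Table 7, hemoglobin: for a subject whose baseline is at least 3.0 g/dL above the lower limit of normal, one confirmed value can meet both the fall trigger and, read literally, the release condition

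*Protocol*

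**What the plan says.** The hemoglobin row of Table 7 (Protocol 6.1.7) has two mandatory triggers.

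- Absolute: "If hemoglobin < 8 g/dL, interrupt study drug dosing and confirm by repeat testing with new sample".
- Relative: a decrease of at least "3.0 g/dL from baseline without an alternative etiology, interrupt study drug dosing and confirm by repeat testing with new sample".

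A further bullet leaves continuation to the investigator when the cause of such a fall is known; that bullet is not at issue here.

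The last bullet governs release after either trigger: "If confirmed, continue to withhold study drug until hemoglobin value returns to normal reference range or its baseline value". Its two alternatives are joined by *or*, so either is enough.

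Appendix N grades hemoglobin under the item "K1. Hgb (g/dl) decrease from pre-treatment", and its Grade 4 entry is "≥ 3.0; or Hgb < 7.0". A fall of 3.0 g/dL is therefore Grade 4 at any absolute level. SAP Appendix A repeats this grading.

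The entry rule in Protocol 5.2.2 excludes "Hemoglobin < 10 g/dL" and sets no upper limit, so subjects with high-normal baselines are eligible.

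**The concern.** The relative trigger looks only at the distance from baseline. The first release alternative looks only at the reference range. Nothing in the row links the two, so a subject who starts high enough can meet both with one value. The row then tells the site to withhold and, read literally, that the condition for ending the hold is already satisfied.

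At stake is consistent handling of a mandatory safety hold. The protocol calls the fall Grade 4 and lists anemia among its adverse events of special interest (6.1.1.3). On the same confirmed result, one site could restart at once and another could hold until hemoglobin is back at baseline, each with a defensible reading of the row.

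**Working it through.** This is a check of logic. The plan states no figure to reproduce.

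**Inputs.** B is the subject's baseline, H the confirmed current value and L the LLN. The trigger and release come from Table 7. The documents give no hemoglobin reference range, so L is an assumption, varied from 11.5 to 13.5 g/dL.

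**Conditions.**
- Relative trigger: H ≤ B − 3.0.
- Release: H inside the reference range (for a fall, H ≥ L), or H back at B.
- The baseline alternative cannot hold together with the trigger, because H is at least 3.0 below B.
- The range alternative and the trigger hold together when L ≤ H ≤ B − 3.0. Such a value exists if and only if B ≥ L + 3.0.

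**Lowest baseline at which the overlap is possible.**

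| Assumed L (g/dL) | L + 3.0 (g/dL) |
|---|---|
| 11.5 | 14.5 |
| 12.0 | 15.0 |
| 12.5 | 15.5 |
| 13.0 | 16.0 |
| 13.5 | 16.5 |

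The overlap exists for any L; only the cut-off moves.

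**Examples.**
- L = 13.0, baseline 16.5, confirmed 13.5: the fall is 16.5 − 13.5 = 3.0, so the trigger is met at Grade 4. Since 13.5 ≥ 13.0, the range alternative is met too.
- Baseline 14.0, confirmed 11.0: the fall is again 3.0, but 11.0 is below every assumed L. The row works as written.
- The below-8 trigger: a value under 8 is below every assumed L, so there is no overlap unless the subject's own baseline is below 8, which the 10 g/dL screening limit makes unlikely.

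**Width of the overlap.** It spans (B − 3.0) − L. At B = L + 3.3 that is 0.3 g/dL. A larger fall leaves the range and the conflict disappears.

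**Comparison with other rows of Table 7.** The neutrophil, lymphocyte, white-cell and platelet rows use similar release wording, but their triggers are fixed low cut-offs. The creatinine row is the other one with a baseline-relative trigger. It requires more than 1.5 times baseline together with a value above the upper limit of normal (ULN), and restarts only when the value is at or below both limits, so trigger and restart cannot both hold. Only the hemoglobin row pairs a trigger based on baseline alone with a release that the reference range alone can satisfy.

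**Frequency.** The share of subjects with a high enough baseline is P(B ≥ L + 3.0) / P(B ≥ 10). Take a normal baseline with assumed mean 12.5 to 14.0 and SD 1.2 to 1.5, cut off at 10, and L from 11.5 to 13.0. The share then runs from 0.2% (mean 12.5, SD 1.2, L 13.0) to 37% (mean 14.0, SD 1.5, L 11.5). That range is too wide to be informative. It also counts subjects who could be exposed to the overlap, not subjects who have a confirmed, unexplained, in-range fall.

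**The case against.** The strongest reply is linguistic. A value that never left the reference range cannot return to it, so for an in-range fall only the baseline alternative is left. The literal reading would also make the instruction to keep withholding after confirmation empty for these subjects, which is a reason to doubt it. This is a plausible reading and may be what was meant. But the row does not state it, and the text supports the other reading as well.

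A second reply is that other text limits the harm. Section 6.1.7 asks for investigator assessment, standard of care and follow-up of clinically significant results, and caps interruptions for adverse events at 7 consecutive days up to Week 24 and 30 days afterwards, with an investigator decision on restarting beyond 30 days. Section 5.4.1 provides for withdrawal on clinically significant laboratory results. All of this stands, and it bounds how far sites could diverge. None of it says what ends this particular hold.

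Three stronger inferences are tempting and not supported.

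- *The release bullet cancels the trigger.* It does not. Interruption and the repeat sample still happen, and the row works as written for every baseline below L + 3.0.
- *Exposure results become site-dependent.* Protocol 8.1.2.3 defines exposure as last dose date minus first dose date plus 1 day, so a temporary hold generally leaves it unchanged unless it becomes permanent or falls at the end of treatment. SAP 8.1 does not say that interruptions are subtracted. Tablet compliance (SAP 8.2) is summarised for Period 1 only, and SAP 11.1 records that Period 1 reporting is complete.
- *Phase 2 shows in-range falls to be expected.* The Introduction says that at higher doses "there was a reduction in mean hemoglobin; however, the mean hemoglobin levels remained within normal range throughout the treatment period". That concerns means, in a passage on subjects with hsCRP above the ULN, and does not show individual falls of 3.0 g/dL. The preceding sentence reports improved mean hemoglobin relative to placebo at 3 mg and 6 mg BID. Section 5.6.4 matches 6 mg BID on daily AUC with 15 mg QD, the dose all subjects receive from Amendment 6.

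**Conclusion.** The point holds as a conflict within one stated safety rule. For any subject with baseline at or above LLN + 3.0 g/dL, a confirmed value can meet the fall trigger and, read literally, the release condition. A second defensible reading gives the opposite action, and the row does not choose between them.

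The scope is narrow: high-normal baseline, confirmed unexplained fall of at least 3.0 g/dL, value still in range. The conclusion depends on no particular LLN. How often it happens is unknown, because the documents give no reference range, baseline distribution or event rate. It has no bearing on the completed Period 1 efficacy analysis; the practical benefit is to subjects still being dosed in Period 2.

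**What to change.** The sponsor should reconcile the hemoglobin trigger and release bullets in Table 7 by stating which release condition applies after a value below 8 g/dL and which after a fall of at least 3.0 g/dL from baseline. Any explicit statement, whichever condition it names, would remove the double reading. The choice is clinical and belongs to the sponsor's medical team; none is proposed here. The creatinine row shows that the protocol already writes a baseline-relative trigger and its restart so that they cannot both hold, and is cited only as an example of form.

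The cost is one sentence at the next amendment or in a letter to investigators, with no added tests or visits and no change to the SAP.
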